8.4.2 Quantitative Analyses

Psychometric and Validity Analyses

Psychometric analyses of the responses of the expected ~10-15 male and ~10-15 female participants who will complete evaluation of the three products will be conducted. We will start the analyses by examining the individual item characteristics for items that have been adapted from our previous USPE scales for use as rectal USPE scales to measure the products used in this trial. We will first conduct an initial examination of means, standard deviations and endorsement level for each item. We will then examine the component structure (internal validity) of each of the adapted scales using principal component analyses to conduct these exploratory dimensional analyses. We will also calculate internal consistency values (Cronbach's Coefficent Alpha statistic) for each of these newly adapted scales for each of the evaluated formulations. In addition, we will conduct exploratory dimensional analyses using principal component analysis to examine the additional items that have been added to the original pool of items in anticipation of unique physicochemical and rheological properties hypothesized to be associated with the rectal environment and suppository formulations, and also to measure any hypothesized USPE scales that we expect to be unique to these experiences. These analyses may result in new and unique additional USPE scales. A series of paired sample t-tests comparing each product pair will then be conducted on the scores from all USPE scales for the males and females separately, and also as a combined sample. See section 8.2.4 and 8.2.5 for associated effect size and power analysis considerations.

Sociodemographic and Individual Product Comparisons

We will first provide an overall description of the sample of participants using means, standard deviations and percentages, as appropriate, to examine demographic variables such as age, sex, and race/ethnicity, as well as sexual/reproductive history variables. After conducting the psychometric analyses, we will also calculate scale scores associated with the USPE scales being evaluated and compare them as noted in 2.1.1(2) above. These scores will be considered in relation to the biophysical measures associated with the formulations being evaluated. Specifically, we will quantitatively examine responses on the pre-existing and adapted/new user perception scales, within both females and males, for perceptual differences between products on the different scales using paired t-tests. Given our small sample size and the new context of the study parameters, we will not apply a correction for the number of statistical tests conducted, to guard against Type II statistical errors. We will also calculate effect sizes for each product comparison as a Cohen's d statistic.³⁴ Secondary analyses that examine group differences (e.g., age, race/ethnicity, etc) across behavioral dimensions and formulation ratings will also be conducted, using independent t-tests, analysis of variance, and Pearson correlations, as appropriate, and as data allows. Further, other quantitative data may be used (e.g., USPE scale scores and their statistics; willingness-to-use; pairwise comparisons) to stratify participants in the qualitative data to determine whether themes and patterns vary as a function of those variables.

9. Data Handling and Record Keeping

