4.5 Required Medications and Procedures

Condoms are recommended for use by participants enrolled in this study and will be strongly encouraged for all sexual encounters during the study period. Natural oils can reduce the integrity of latex condoms: since both suppositories contain natural oil(s), the study will provide non-latex condoms to participants in quantities expected to be sufficient for the study period. These condoms will not be impregnated or coated with any type of spermicide. In the event that a participant needs additional condoms between visits, s/he may request these from the study at any time.

5. Study Product Regimen

The products will be evaluated by male and female participants during receptive anal intercourse (see Section 6.3, Formulation Evaluation) and vaginal-penile intercourse (females only). No product used in this study will include any anti-HIV compounds or drugs. During each of three study periods (between visits 2 and 3, 3 and 4, and 4 and 5), participants will evaluate one formulation. Each formulation will be

evaluated by each participant, namely: HEC gel, Zetpil® suppository, and Key-E® suppository. The ordering of product presentation will be randomized (see section 6.2 below). Participants will be blind to formulation (each product will be assigned a color and will be referred to as such, (e.g., ‘the orange product’; see §1.3.2). Study staff, including study clinicians and research staff, will not be blind to participant product assignments.

6. Study Procedures / Evaluation

See APPENDIX A: Schedule of Visits and Procedures

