6.4 Formulation Evaluation (Visits 2-5)

6.4.1 Randomization to Product Presentation Order

Once a participant has been successfully screened for STI/HIV and pregnancy and remains interested in participating in the study, s/he will be scheduled for Visit 2 and assigned to a randomized product evaluation order. There are 6 such orderings: (1) HEC, Zetpil®, Key-E®; (2) HEC, Key-E®, Zetpil®; (3) Zetpil®, HEC, Key-E®; (4) Zetpil®, Key-E®, HEC; (5) Key-E®, HEC, Zetpil® (6) Key-E®, Zetpil®, HEC). Approximately 3-5 participants (~2 males and ~2 females) will be randomly assigned to each possible assignment order. If, for any reason, the participant does not enroll in the study after randomization, their assigned product order will be re-assigned to another participant.

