Participants who have not engaged in RAI/VI with study products and completed a web-based survey (i.e., product evaluation activities) after ~10 days will be contacted by the study team to ensure that they understand the study requirements and are still willing and able to comply. If a participant still has not completed product evaluation activities after ~20 days, they will be contacted again by the study team to again discuss whether they are willing and able to continue participating in the study. If a participant has not completed a product evaluation web-based survey after ~28 days, they may be withdrawn from the study (at the discretion of the PI or designee, depending on the individual circumstances of the participant). Participants who voluntarily withdraw from the study or who are withdrawn for safety or protocol compliance reasons will be replaced, if the study timeline allows. That is, given study timeline availability, additional participants will be enrolled to reach approximately 20-30 completed participants.

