8.3.3 Statistical Considerations

Given the planned sample size (n~20-30), and the formative nature of this research, statistical comparisons between products are not the most important aim of this study. However, assuming the larger sample size (i.e., 24-30, 12-15 males and 12-15 females) is achieved and conditions for USPE scale comparisons are met (i.e., analyses indicate good psychometric properties of existing scales, such that we confirm each scale's internal validity by verifying high item scale loadings and we find good internal consistency for a specific scale as measured by the Coefficient Alpha statistic), we will compare products and compute the effect sizes for all of the comparisons of each formulation between sexes (i.e., given 12-15 males and 12-15 females), between compartments (females), and between formulations to provide guidance for outcomes interpretation and for future studies. While we do not expect all comparisons between products to be statistically significant as the relatively small sample size places limits on statistical power, we do anticipate that some comparisons may be statistically significant based on our past research into scale score comparisons conducted on a number of different products. For example, with respect to sexual activity scales in our previous study among a sample of 24 heterosexual couples using vaginal formulations and engaging in vaginal-penile sex, effect sizes resulting in significant differences in pair-wise comparisons of 3 different formulation conditions ranged from 0.60 (considered a medium effect size) to 2.67 (considered a very large effect size). In Project DRUM (section 1.1a), among a sample of 15 (8 male; 7 female) participants using rectal formulations and engaging in receptive anal intercourse, effect sizes ranged from small to medium.

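### Section 8.4.2 compares products from a randomised six-order, three-period crossover with no period term; if scores drift, power falls and Cohen's d shrinks (minor, cheap to fix)

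*Combined protocol and SAP*

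**What the plan says.** Section 5 has every participant evaluate one formulation in each of three study periods and states: "The ordering of product presentation will be randomized". Section 6.4.1 lists the six orders and says: "Approximately 3-5 participants (~2 males and ~2 females) will be randomly assigned to each possible assignment order". It describes no blocking or stratification. Under section 7.1.4, participants who withdraw "will be replaced, if the study timeline allows", and nothing says that a replacement takes the same order.

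Section 8.4.2 gives the product analysis: "A series of paired sample t-tests comparing each product pair will then be conducted", for each sex separately and for both combined. It later repeats that scale responses will be examined "for perceptual differences between products on the different scales using paired t-tests". It also plans to "calculate effect sizes for each product comparison" as Cohen's d, without naming the denominator. On multiplicity it says: "we will not apply a correction for the number of statistical tests conducted, to guard against Type II statistical errors". Analysis of variance appears only for group differences such as age or race/ethnicity. Period and order are not named anywhere in section 8.

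Section 2.1.1 places the pairwise comparisons and their effect sizes within the second primary endpoint. Section 8.3.3, however, says that "statistical comparisons between products are not the most important aim of this study" and makes them conditional on reaching 24-30 participants and on good psychometric results.

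**The concern.** The plan randomises order and then leaves it out of the analysis. Ratings could change over successive evaluations, for example as participants get used to the surveys or to product insertion. A paired t-test treats any such change as random variation between participants. The SD of the differences grows, and with it the threshold for detecting a product difference, while d gets smaller.

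This matters for two reasons taken from the plan itself. It forgoes multiplicity correction to avoid missing real differences, so it should not leave removable variation in the error term. It also wants the effect sizes to inform interpretation and later studies, and a d diluted by drift would be a poor guide to those.

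**Working it through.** **Inputs from the documents.** Three periods and six orders (sections 3, 5 and 6.4.1); product comparisons at 24-30 participants, 12-15 per sex (section 8.3.3).

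**Assumed, because the documents give none.** Score SD 1; within-person correlation ρ = 0.5 (range 0.3-0.7); linear drift δ of 0, 0.1, 0.25 or 0.5 SD per period, the last being a stress case; true product difference 0.5 SD; two-sided 5% level.

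**Plan's own figures.** The plan derives no power. Its allocation figure is consistent: 20/6 = 3.3 and 30/6 = 5.0 participants per order, matching its 3-5.

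**Drift in the paired difference.** Across the six orders, the two products of any pair are -1, -2, 1, 2, -1 and 1 periods apart. The mean gap is 0 and the mean square is (1+4+1+4+1+1)/6 = 2. Without drift, the variance of the difference is 2(1-ρ) = 1. Drift adds 2δ². With evenly filled orders:

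- Standard-error ratio = √(1 + δ²/(1-ρ)).
- d shrinks to 1/ratio of its value if standardised by the SD of differences, or to 1/√(1 + 2δ²/3) if by the pooled SD.
- Power at n=24 comes from the noncentral t with 23 df and noncentrality 0.5√24/ratio = 2.449/ratio. Power at n=12 was simulated.

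| Drift per period | SE ratio | Loss in d (SD of differences) | Loss in d (pooled SD) | Paired-t power, n=24 | Paired-t power, one sex, n=12 |
|---|---|---|---|---|---|
| 0 | 1.000 | 0% | 0% | 0.65 | 0.35 |
| 0.1 | 1.010 | 1% | 0.3% | 0.64 | 0.35 |
| 0.25 | 1.061 | 6% | 2% | 0.60 | 0.30 |
| 0.5 | 1.225 | 18% | 7% | 0.48 | 0.20 |

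Simulation at n=24 (20,000 trials per setting) gave 0.657, 0.645, 0.606 and 0.472. For ρ from 0.3 to 0.7, the SE inflation is 4-10% at drift 0.25 and 17-35% at drift 0.5. A single shift s after the first product has mean-square gap 2s²/3, so the ratio is only 1.021 at s = 0.25 and 1.080 at s = 0.5.

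**With period adjustment, n=24.** A participant + product + period model (44 df) has power 0.669 at every drift. Regressing each participant's product difference on the period gap gave simulated power 0.650-0.655. About 0.02 of the pooled model's advantage therefore comes from its extra degrees of freedom; the rest is due to period.

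**If orders are not filled evenly by design.** Under unrestricted randomisation the gaps vary by chance, so the true variance of the mean difference is (1 + 2δ²)/n. At δ = 0.5 and n=24 the true standard error is √(1.5/24) = 0.25, which is what the paired t-test reports (simulated: reported 0.247, actual 0.248). With even orders the true value is √(1/24) = 0.204 while the test still reports about 0.25. The loss of power occurs either way. For a difference of 0.60 at drift 0.5, unrestricted allocation gave 63% with the paired t-test and 80% with the pooled period model.

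**Bias from unequal orders.** The bias is drift times the difference in the two products' mean periods. If order counts differ by at most one, that difference is 0 at n=12, 24 or 30, and at most 0.27 in one sex of 15, giving 0.27 × 0.25 = 0.07 SD at drift 0.25. If each sex of 15 is filled separately, the combined n=30 has a typical (root-mean-square) difference of 0.09, giving 0.09 × 0.25 = 0.02 SD. Replacing one withdrawal into another order gives at most 0.33 in a sex of 12 (0.08 SD) or 0.17 in 24 (0.04 SD).

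**The case against.** The case for leaving the plan alone is substantial. Randomised order already protects the comparison. No drift is documented, products are only about two weeks apart, and at 0.1 SD per period the effect is negligible. Sections 1.2 and 8.3.1 say that standard hypothesis testing is not an appropriate endpoint, and section 8.3.3 ranks product comparisons below other aims. All of this stands, and it limits the importance of the point.

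A reader might go further and infer that the paired t-tests are biased or produce false positives. The documents do not support that. With even orders the mean difference is unbiased and the test is conservative: simulated Type I error at n=24 was about 3.5% at drift 0.25 and 1.8% at 0.5. A reader might also infer that the standard error is always too large. That needs near-even filling, and section 6.4.1 neither specifies blocking nor rules out unrestricted randomisation, under which the standard error is about right.

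A further objection is that the usual remedy, the pooled participant + product + period model, has a weakness of its own. It assumes similar residual variance across products. With one product at twice the residual variance, its simulated 95% intervals covered about 93-94% for pairs with that product; at four times, about 92%. The paired t-test stayed at 95% in the fourfold case. Switching models when variances look different would be a data-driven choice repeated over 25 scales (5 + 6 + 14 in section 2.1.1). This objection also stands, and it decides the form of the fix.

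**Conclusion.** The point holds in a limited, conditional form. If scores drift over periods, the planned analysis loses power and reports a smaller d, whichever way the orders were filled. Whether the standard error is also overstated depends on even filling. Under the stated assumptions the loss is trivial at 0.1 SD per period, modest at 0.25 (0.05 in power at n=24), and considerable only in the 0.5 stress case. Bias from unequal orders is nil with even filling, such as 4 or 5 per order at n=24 or 30, and otherwise small. The drift, correlation and true difference are all assumptions. Importance is minor: this is an inexpensive improvement to a formative study, and the planned test is not invalid.

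**What to change.** In section 8.4.2, keep the paired t-tests and add the following, pre-specified for every scale and not chosen after looking at the variances:

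- For each product pair, overall and by sex, regress the participant's product difference on period and report the intercept as the period-adjusted difference with a 95% CI. Use two period-indicator differences, or the single period gap if linear drift is assumed and stated. With even orders the gap version removes only 75% of the extra variance from a one-off shift. Neither version needs equal residual variance across products.
- Use the same regression for women's vaginal scores, where only the two suppositories are compared.
- A participant + product + period model may be reported as well, stating that it assumes similar residual variance.
- State the denominator of Cohen's d, and report the number of participants in each order by sex.

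No new data are needed. The cost is some extra analysis and one or two degrees of freedom per comparison. With no drift and even orders, intervals widen by the ratio of t quantiles. At n=12, one degree of freedom costs 2.228/2.201 = 1.2% and two cost 2.262/2.201 = 2.8%. At n=24 the costs are 0.3% and 2.080/2.069 = 0.5%. Uneven orders add to this, most noticeably in one sex of 12, which is another reason to keep the paired t-test alongside.

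### Effect sizes intended to guide later studies are planned as point values of Cohen's d, with no confidence interval and no small-sample bias correction

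*Combined protocol and SAP*

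**What the plan says.** Primary endpoint 2 in section 2.1.1 has the averaged scale scores evaluated psychometrically, then used for pair-wise comparisons with effect sizes. Section 8.4.2 fixes the statistic for product comparisons: "We will also calculate effect sizes for each product comparison", with Cohen's d as the measure. The same paragraph examines the scales "for perceptual differences between products on the different scales using paired t-tests", so these contrasts are within person. Group differences are handled "using independent t-tests, analysis of variance, and Pearson correlations, as appropriate, and as data allows".

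Section 8.3.3 widens the set of effect sizes. If 12 to 15 participants of each sex are reached and the scales perform well, "we will compare products and compute the effect sizes for all of the comparisons of each formulation between sexes", and also "between compartments (females), and between formulations to provide guidance for outcomes interpretation and for future studies". It names no statistic for the sex and compartment contrasts.

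Neither section mentions a confidence interval, a small-sample correction or the SD that serves as divisor. For effect-size and power considerations, section 8.4.2 refers the reader to sections 8.2.4 and 8.2.5. Neither exists, because section 8.2 ends at 8.2.2. Section 8.3.3 is the likely target and contains no formula.

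**The concern.** Sections 1.2 and 8.3.1 set hypothesis testing aside as an endpoint, so the standardised differences are the natural way to summarise how products, compartments and sexes compare. Section 8.3.3 gives them a forward use: "to provide guidance for outcomes interpretation and for future studies".

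Two properties of a bare Cohen's d matter for that use at these sample sizes. It is biased away from zero, and the bias carries into any sample size computed from it. It is also very imprecise, and a point value hides this. A reader who sees 0.5 for one scale and 0.2 for another cannot tell whether the data separate them.

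A lesser issue is that the divisor is not stated. Paired and independent contrasts can be standardised by different SDs, and the values cannot be converted without the within-person correlation.

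**Working it through.** **Inputs from the documents.** Sample sizes are 12 to 15 per sex and 24 to 30 combined, the condition in section 8.3.3. Product contrasts are paired (section 8.4.2) and sex contrasts are independent (section 8.3.3).

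**Assumptions.** Score differences are normal, d = 0.5 is an illustrative observed value, and intervals are two-sided 95%. The within-person correlation r is not in the documents, so a range is shown.

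**The plan's own figures.** There is no sample-size or precision calculation to reproduce. The only numerical effect sizes are 0.60 to 2.67, for significant pair-wise comparisons in an earlier study of 24 couples (section 8.3.3). They come from outside data and can only be checked for consistency. The smallest paired difference-SD d significant at two-sided 0.05 (assumed) with n=24 is t(0.975, 23)/√24 = 0.42. On the raw-score SD with r=0 it is 0.42 × √2 = 0.60, and for 24 against 24 independent people it is 0.58. The stated lower limit fits all of these, so it does not show which SD the research team uses.

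**Step 1: bias.** The correction factor is J = 1 − 3/(4·df − 1), with df = n − 1 for a paired d. On average d overstates the true value by 1/J. Required sample size varies as 1/d², so it is understated by 1/J².

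| Paired n | J | Overstatement of d | Factor on required n |
|---|---|---|---|
| 12 | 1 − 3/43 = 0.930 | 7.5% | 1.16 |
| 15 | 1 − 3/55 = 0.945 | 5.8% | 1.12 |
| 24 | 1 − 3/91 = 0.967 | 3.4% | 1.07 |
| 30 | 1 − 3/115 = 0.974 | 2.7% | 1.05 |

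For the sex contrast df = 2n − 2. J is 0.965 with 12 per sex and 0.973 with 15 per sex, an overstatement of 3 to 4%.

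**Step 2: precision.** For a paired difference-SD d, t = d√n. Find the two noncentrality values that put the observed t at the 97.5th and 2.5th percentiles of the noncentral t distribution, then divide by √n. For independent groups, t = d/√(2/n) and the limits are multiplied by √(2/n).

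| Contrast, observed d = 0.5 | t | 95% CI |
|---|---|---|
| Paired, n=12 | 1.73 | -0.11 to 1.09 |
| Paired, n=15 | 1.94 | -0.05 to 1.03 |
| Paired, n=24 | 2.45 | 0.07 to 0.92 |
| Paired, n=30 | 2.74 | 0.12 to 0.88 |
| Male v female, 12 per sex | 1.22 | -0.32 to 1.31 |
| Male v female, 15 per sex | 1.37 | -0.23 to 1.22 |

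Within one sex the interval runs from below zero to well above 0.60, the value that section 8.3.3 calls medium.

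**Step 3: divisor.** With equal SDs, difference-SD d divided by average-SD d equals 1/√(2(1 − r)).

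- r = 0.2: 1/√1.6 = 0.79
- r = 0.5: 1/√1.0 = 1
- r = 0.8: 1/√0.4 = 1.58

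An average-SD d of 0.50 would therefore read as about 0.40, 0.50 or 0.79. The direction depends on r.

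**The case against.** The strongest reply is that this is a formative instrument-development study. Section 8.3.3 ranks product comparisons below its other aims, makes the wider set of effect sizes conditional on sample size and scale quality, and admits that small numbers limit power. Section 8.4.2 begins with item statistics, component structure and internal consistency. Each product d also accompanies a paired t-test, so a reader given t and n could recover a difference-SD d and its interval. All of this stands, and it limits the weight of the point. It does not supply the interval or the correction.

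Four stronger readings are tempting but unsupported:

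- **Effect sizes are the main quantitative output.** They are one named part of primary endpoint 2, after the psychometric work.
- **The plan puts product, compartment and sex contrasts on incompatible versions of Cohen's d.** Cohen's d is named only for product comparisons. For the others no statistic is given, so the divisor is unspecified rather than wrong.
- **The choice of divisor will make later studies too small.** For a paired study, difference-SD d is the quantity needed for sizing, and the ratio in step 3 goes either way with r. Understatement is shown only for the small-sample bias.
- **Noise will be reported under size labels.** The remark that "effect sizes ranged from small to medium" describes the earlier rectal gel study. It is not a reporting rule for this one.

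**Conclusion.** The point holds as an improvement to the analysis plan, not as an error in any stated figure. The missing interval is the larger part: at 12 to 15 per sex a paired d of 0.5 is compatible with no difference and with a value above 1, and even at n=30 the interval is 0.76 wide. The missing correction is real but modest, as the table in step 1 shows. The unstated divisor is missing detail that should be filled in; it does not carry the point alone.

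The sizes assume normal differences and the sample sizes in section 8.3.3. The paired intervals apply to the difference-SD version of d. The r values are assumptions with no source in the documents.

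**What to change.** In section 8.4.2, replace Cohen's d with Hedges' g and a 95% confidence interval for each product comparison. In section 8.3.3, apply the same to the sex and compartment effect sizes. For each contrast type, state the SD used as divisor, and report the within-person correlation for paired contrasts so that paired and independent values can be converted. Correct the cross-reference to sections 8.2.4 and 8.2.5.

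The choice between difference SD and average SD can stay with the study team. Difference SD has an exact interval and serves directly for sizing paired studies. Average SD is closer in scale to the pooled SD of the sex contrasts, but its interval depends on the estimated correlation and needs an approximation or a bootstrap.

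The change is a little code and a few lines of text, with no new participants or procedures. The downside is slightly smaller effect sizes and visibly wide intervals.
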